In recent clinical trials of Ebola virus vaccine candidates using ChAd3 as the vaccine vector (a group C Ad, like ChAd155), there were no vaccine-related SAEs. Most AEs were mild (Grades 1-3) and self-limited, resolving within 48 hours after vaccination. The most common systemic AEs were fatigue and headache. All abnormal lab values recorded during these studies were Grade 1, with the most common abnormalities being transient lymphopenia, anemia, or thrombocytopenia that developed on Day 1 after vaccination, and which had resolved by Day 7 after vaccination.⁹⁻¹² Similar findings were reported for a novel ChAd3-vectored HCV vaccine,¹⁴ as well as multiple malaria vaccine candidates that used ChAd63 (a group E adenovirus) as the vaccine carrier.¹³ A small number of participants in each of the ChAd3 Ebola vaccine studies (<5 in each study) developed asymptomatic prolongation of the activated partial thromboplastin time (aPTT) which resolved by the end of the follow-up period.⁹⁻¹² In one of the trials, further investigation of the prolonged aPTT revealed induction of an antiphospholipid antibody.¹²

The ChAd155 vector being used in this trial has been previously tested in humans in a Phase 1 trial of a novel RSV vaccine candidate.²² The vaccine dosages used in that study (low-dosage, 5×10^9 vp; high-dosage, 5×10^{10} vp) were half of those proposed in this trial. Per the investigator's brochure for ChAd155-RG, in that previous study, there were no vaccine-related SAEs, and the most common AEs were local injection site pain (100% of vaccine recipients vs. 5.3% of placebo recipients), fatigue (50% of high-dosage (5×10^{10} vp) vaccine recipients, only 1 subject or 3% with Grade 3 fatigue) and headache (34.5% of high-dosage vaccine recipients).

In recent studies of COVID-19 vaccines that use an adenovirus vector, there were a small number of individuals who experienced rare but serious thrombotic events, including cerebral

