7.4.5. Visit 06, Day 22 (window: +2 days), Fourth Vaccination

- If a subject has a positive symptom screen prior to the visit (per the MOP), viral testing may be performed during this study visit with a research-based assay

- Review medical history to assure continued eligibility.
- Review eligibility criteria with subjects, and review results of all safety lab evaluations, before vaccination to assure continued eligibility for vaccination.
- Review all concomitant medications for accuracy and completeness. Any new medications or vaccinations will be recorded and assessed for continued eligibility.
- Obtain vital signs including oral temperature, blood pressure, and pulse.
- Perform a targeted physical examination, if indicated based on review of complete medical history.
- Examine vaccination site for local reactions before vaccination and determine whether information recorded by subjects on the memory aid conforms to examination.
- Collect blood for safety labs (chemistry and hematology), immunogenicity (RFFIT assay), and developer assays before vaccination.
- Perform a urine pregnancy test within 24 hours before fourth vaccination on all female subjects of childbearing potential. Results must be negative and known before fourth vaccination.
- Perform pre-administration reactogenicity assessments before the fourth vaccination to establish baseline. Subjects will then receive a single dose of vaccine via IM injection into the deltoid muscle of the arm opposite to that of the third injection. The site of injection (right or left arm) and time of administration will be recorded on the appropriate eCRF.
- Observe subjects in the clinic for ≥ 30 minutes after vaccination to monitor for any acute reactions.
- Evaluate the vaccination site and assess for reactogenicity and AE/SAEs for ≥ 30 minutes after vaccination and before discharge from clinic and record on the appropriate CRF.
- Subjects will enter their reactogenicity information on a memory aid. Subjects will be provided a thermometer, ruler and memory aid and will record daily oral temperature, solicited injection site and systemic reactions, any unsolicited AEs, and concomitant medications. Subjects will be asked to bring their memory aid with them at their next study visit.
- Assess all AE/SAEs and new onset chronic medical conditions, then record them on the appropriate eCRF.

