7.7. Unscheduled Visit

Unscheduled visits may occur at any time during this trial. Labs may be drawn at PI discretion. Any of the following activities may be performed:

- If an unscheduled visit occurs \leq 14 days after any study vaccination, the subject will undergo a symptom screen prior to the visit, and if the screen is positive (per the MOP), viral testing may be performed during this visit with a research-based assay
- Obtain interim medical history, including an assessment for new medical conditions by interview of subjects and note any changes since the previous clinic visit or phone call.

- Record all concomitant medications on the appropriate eCRF (if before 28 days after the last vaccination).
- Obtain vital signs including oral temperature, blood pressure, and pulse.
- A targeted physical examination will be performed, if needed, by a study clinician licensed to make medical diagnoses and listed on Form FDA 1572 as the site PI or sub-investigator, if indicated based on review of complete medical history.
- Examine vaccination site for local reactions if visit occurs ≤ 28 days after any vaccination, and if so, determine whether information recorded by subjects on the memory aid conforms to examination.
- Obtain blood for safety if needed.
- Perform a urine pregnancy test on all female subjects of childbearing potential (if indicated)
- Assess all AE/SAEs and new onset chronic medical conditions and associated concomitant medications and record them on the appropriate eCRF.

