### **3.2. Endpoints**

#### **3.2.1. Primary**

- Frequency and severity of solicited injection site and systemic reactogenicity events from the time of each vaccination through Day 7 after each vaccination, in each vaccination group and overall.
- Frequency and severity of SAEs considered study vaccine-related and reported at any time after the first vaccination through the end of the study, in each vaccination group and overall.
- Frequency and severity of study vaccine-related lab AEs through Day 22 from the time of the first vaccination, in each vaccination group and overall.
- Frequency and severity of unsolicited study vaccine-related AEs from the time of the first vaccination through Day 28 after the last vaccination, in each vaccination group and overall.
- Number of subjects with new onset of a chronic medical condition at any time after the first vaccination, in each vaccination group and overall.
- Frequency and severity of any SAEs at any time after the first vaccination through the end of the study, in each vaccination group and overall.

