## 9.6. Clinical Laboratory Evaluations

Clinical safety laboratory parameters will be evaluated after receipt of each study vaccine (on Days 2, 8, 16, and Day 22) and will include WBC, hemoglobin, platelets, absolute neutrophil count, absolute lymphocyte count, ALT, AST, total bilirubin, BUN and creatinine. Grading scales for safety laboratory parameters are presented in [Table 12](#) and [Table 13](#). Baseline values will be the most recent values obtained prior to receipt of the first dose.

The following summaries for clinical laboratory results will be presented:

- Subject listings of abnormal chemistry and hematology results of Grade 1 severity or higher will be presented in [Table 79](#) and [Table 80](#), respectively.
- Frequency and percent of subjects with abnormal chemistry results over all parameters and for each parameter, by visit, vaccination group and severity ([Table 81](#), [Table 82](#), [Table 83](#), [Table 84](#), [Table 85](#), and [Table 86](#)).

- Frequency and percent of subjects with abnormal chemistry results related to study product, over all parameters and for each parameter, by visit, vaccination group and severity ([Table 87](#), [Table 88](#), [Table 89](#), [Table 90](#), [Table 91](#), and [Table 92](#)).
- Descriptive statistics (mean, standard deviation, median, minimum, and maximum) of each chemistry parameter, including change from baseline, by time point and vaccination group ([Table 93](#), [Table 94](#), [Table 95](#), [Table 96](#), and [Table 97](#)).
- Frequency and percent of subjects with abnormal hematology results over all parameters and for each parameter, by visit, vaccination group, and severity ([Table 98](#), [Table 99](#), [Table 100](#), [Table 101](#), [Table 102](#), and [Table 103](#)).
- Frequency and percent of subjects with abnormal hematology results related to Study Product, over all parameters and for each parameter, by visit, vaccination group, and severity ([Table 104](#), [Table 105](#), [Table 106](#), [Table 107](#), [Table 108](#), and [Table 109](#)).
- Descriptive statistics (mean, standard deviation, median, minimum and maximum) of each hematology parameter, including change from baseline, by time point and vaccination group ([Table 110](#), [Table 111](#), [Table 112](#), [Table 113](#), and [Table 114](#)).

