**Table 80: Listing of Abnormal Laboratory Results of Grade 1 or Greater – Hematology\***

### 14.3.5 Displays of Laboratory Results

#### 14.3.5.1 Chemistry Results

**Table 81: Abnormal Laboratory Results by Maximum Severity, Time Point, and Vaccination Group - Any Chemistry Parameter\***

Time Point	Vaccination Group	N	None		Mild/ Grade 1		Moderate/ Grade 2		Severe/ Grade 3		Any Severity	
			n (%)	95% CI	n (%)	95% CI	n (%)	95% CI	n (%)	95% CI	n (%)	95% CI
Baseline (Pre-Dose 1)	Low Dose ChAd155-RG	x	x (xx)	(xx, xx)	x (xx)	(xx, xx)	x (xx)	(xx, xx)	x (xx)	(xx, xx)	x (xx)	(xx, xx)
	High Dose ChAd155-RG (x1)											
	High Dose ChAd155-RG (x2)											
	Combined High Dose a ChAd155-RG											
	RABAVERT											
	Total											
Repeat for:												
Day 2 (1 Day Post Dose 1)												
Day 8 (Pre-Dose 2)												
Day 16 (2 Days Post Dose 3)												
Day 22 (Pre-Dose 4)												
Max Severity Post Baseline												

Note: The “Max Post Baseline” rows indicate the maximum severity of abnormal laboratory results experienced by each subject at any time point post baseline, including unscheduled assessments.  
N = Number of subjects in the Safety Population; n = number of subjects with laboratory values in the respective category.  
a Both high dose groups combined.

Tables with similar format:

---

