#### 14.2.2 Immunogenicity Response Figures by Measure, Vaccination, and Time Point

**Figure 2: Reverse Cumulative Distribution of Rabies Neutralizing Antibodies (VNA) by Time Point and Vaccination Group - Modified Intent to Treat Population\***

[Implementation Note: For preliminary analyses, data collected through the data cut-off date will be displayed. Prior to day 22 the high dose groups are the same, so results are combined. All scheduled time points will be presented in actual figure.]

[figure not shown]
[figure not shown]

Figure with Similar Format:

**Figure 3: Reverse Cumulative Distribution of Rabies Neutralizing Antibodies (VNA) by Time Point and Vaccination Group - Per Protocol Population**

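### The lab maximum-severity row has no Day 22 limit, the Combined High Dose row keeps pooling after Group C's second dose, and SAP 9.6 implies a lab after RABAVERT's third dose that is not scheduled

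*SAP*

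**What the plan says.** **Endpoint.** SAP 3.2.1 defines the lab primary endpoint as "Frequency and severity of study vaccine-related lab AEs through Day 22 from the time of the first vaccination", by group and overall. Protocol 9.4 keeps abnormal results for the scheduled parameters off the adverse event form, so the lab tables are where this endpoint is reported.

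**Max row.** The note under SAP Tables 81, 98 and 99 defines Max Severity Post Baseline as the "maximum severity of abnormal laboratory results experienced by each subject at any time point post baseline, including unscheduled assessments". On late draws, Protocol 7.7 says: "Unscheduled visits may occur at any time during this trial. Labs may be drawn at PI discretion".

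**Combined row.** Tables 81, 98 and 99 carry a Combined High Dose row at every time point, footnoted "Both high dose groups combined". The lab summary-statistics tables (format of Table 93) and the vital-sign tables (115-119) carry it too. For the antibody figures, the Figure 2 note says: "Prior to day 22 the high dose groups are the same, so results are combined".

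**Lab timing.** SAP 9.6 says: "Clinical safety laboratory parameters will be evaluated after receipt of each study vaccine", and lists Days 2, 8, 16 and 22. For Day 22, Protocol 7.4.5 says: "Collect blood for safety labs (chemistry and hematology), immunogenicity (RFFIT assay), and developer assays before vaccination". The Day 8 draw is also before injection (Protocol 7.4.2), and the Day 29 visit (Protocol 7.4.6) lists no safety labs.

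**The concern.** Three features of the lab shells do not match the design they are meant to report.

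1. The per-subject summary row is open-ended while the endpoint closes at Day 22. Results after Day 22 come from draws made at the investigator's discretion, probably in subjects who are unwell, so they are not comparable with scheduled samples.
2. Groups B and C have the same active exposure until Day 15, when C receives a second high dose and B receives placebo. A pooled row at Day 16 or later mixes two regimens. Day 16 is a sensitive place to do so: for trials of a related ChAd vector, Protocol 2.3.1 describes "transient lymphopenia, anemia, or thrombocytopenia that developed on Day 1 after vaccination, and which had resolved by Day 7 after vaccination". At Day 16, C is one day past a second vector dose and B is 15 days past its only one.
3. A reader of SAP 9.6 would believe that labs cover all three RABAVERT doses, when the schedule covers two. The primary objective compares with the three-dose series.

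**Working it through.** The plan gives no figure for this point. The nearest is SAP Table 3, the chance of seeing at least one event, 1 − (1 − p)^N. All 36 cells reproduce; for N=12 and p=10%, 1 − 0.9^12 = 71.8%, as printed. Nothing below depends on it.

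**1. Which tables inherit the Max row.** The note is printed under Tables 81, 98 and 99.
- Chemistry: Tables 82-86 follow Table 81 as similar-format tables. The related-result Tables 87-92 follow by placement, without a separate format statement.
- Hematology: the SAP assigns the formats explicitly. Tables 101-104 and 107-109 take Table 98; Tables 100, 105 and 106 take Table 99.
- Tables 93-97 and 110-114 are summary statistics without this note.

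**2. What can enter after Day 22.** Scheduled safety labs are on Days 2, 8, 16 and 22, the last with a +2-day window, so to Day 24. Under Protocol 7.6, early-termination labs are those of a regular visit in window, and no regular visit after Day 22 has safety labs. That leaves unscheduled draws. If there are none, the row equals the Day 22 maximum.

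**3. Size for one subject.** Take a subject with no qualifying abnormality by Day 22 and one from a later unscheduled draw:
- Groups A and B: 1/14 = 7.1 points
- Group D: 1/12 = 8.3 points
- Group C: 1/10 = 10.0 points

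**4. Pooling.** From Day 16 the combined row has 14 + 10 = 24 subjects, of whom 10/24 = 41.7% have had two doses. The pooled rate is (14·pB + 10·pC)/24. The rates below are assumed, since the documents give none:

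| B | C | Combined row |
|---|---|---|
| 10% | 20% | 14.2% |
| 10% | 30% | 18.3% |
| 10% | 50% | 26.7% |
| 0/14 | 5/10 | 5/24 = 20.8% |

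Elsewhere the SAP stops pooling once the regimens diverge. Table 21 shows NA from Day 22, Table 27 shows NA at Day 29, and Tables 33 and 68 (after Dose 3) omit the column. The lab tables keep the row at Day 16, Day 22 and Max; the vital-sign tables keep it at those points and at every later visit.

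**5. First scheduled lab after each active dose.** Day 8 and Day 22 draws are before injection.

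| Dose | Next scheduled lab | Interval |
|---|---|---|
| Day 1, all groups | Day 2 | 1 day |
| Day 15, Group C | Day 16 | 1 day |
| Day 8, Group D | Day 16 | 8 days |
| Day 22, Group D | none | – |

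Planned active doses: 14×1 + 14×1 + 10×2 + 12×3 = 84. Those with no later scheduled lab: 12, all third RABAVERT doses; 12/84 = 14.3% of all active doses and 12/36 = one third of RABAVERT doses.

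**The case against.** The strongest reply is that the endpoint is reported. Tables 87-92 and 104-109 give related results by visit, group and severity; their scheduled time points end at Day 22; and the two high-dose groups have their own rows. This stands. A reader might infer from the open-ended Max row that the lab tables fail to estimate the primary endpoint, and the documents do not support that. What is missing is a per-subject maximum confined to the endpoint window.

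Protocol 11.4.3 can also be cited for the Max row, since it takes each subject's worst grade over the follow-up period. It does not define that period for labs, and the endpoint does, so the row still needs an end date. Late values are already visible: Tables 79-80 give the actual study day, and Listings 14-15 include unscheduled draws. In the related-result tables a late value counts only if judged related.

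On pooling, the combined row is additional. In the 5/10 example, 50% is printed in Group C's own row, so nothing is hidden. The Figure 2 note, read literally, would permit pooling at Day 16. But it governs antibody results, whose Day 15 sample is before injection and whose next sample is Day 22. In effect it stops pooling at the first sample after divergence, which for labs is Day 16. SAP practice is not uniform, since Table 52 still combines the groups at Dose 4.

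On RABAVERT, the endpoint itself ends at Day 22, so a missing later lab cannot show that the tables miss it. Nor does RABAVERT have fewer scheduled draws: every arm has the same four. The SAP 9.6 sentence lists the exact days, and Protocol 8.2.1 states the schedule without the word each. The description of early, transient changes comes from ChAd3 trials and says nothing about RABAVERT.

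**Conclusion.** The point holds as three bounded corrections.

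- **Max row:** wrong as written against the endpoint window. The effect is zero if no unscheduled lab is drawn after the Day 22 visit. Otherwise it is 7.1 to 10.0 points in an arm's rate per subject who enters only that way. The documents do not indicate how many such draws to expect.
- **Combined row:** from Day 16 it averages one-dose and two-dose subjects in the ratio 14:10 and describes no single regimen. Group estimates are unaffected. The pooled percentages shown rest on assumed rates and full planned enrolment.
- **SAP 9.6:** its wording and the visit schedule contradict each other and must be reconciled. Under the current schedule, RABAVERT's scheduled labs cover doses 1 and 2 only, which limits the lab comparison with the three-dose series.

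A reader might also infer that between-arm lab statements should rest on Days 2 and 8, when every arm has had one active dose. That would discard Days 16 and 22, the only scheduled labs after Group C's second dose, from an endpoint that runs through Day 22. The trial is descriptive (Protocol 11.1), so no test, power or sample size is affected.

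**What to change.** 1. Define Max Severity Post Baseline, at least in the related-result Tables 87-92 and 104-109, as the maximum through the Day 22 visit including its window, counting unscheduled draws up to then. Leave later unscheduled values to Tables 79-80 and Listings 14-15, which already exist.
2. Set Combined High Dose to NA from Day 16 onward and in the Max rows of the lab and vital-sign tables, as Tables 21 and 27 do for antibody results.
3. Reconcile the SAP 9.6 wording with the visit schedule and, with the schedule as it stands, footnote the lab tables to say that RABAVERT labs cover doses 1 and 2 only.
4. While editing the shells, check the Day 16 label. It reads two days after Dose 3, but by the counting used for Day 2 (one day after Dose 1) it is 16 − 15 = 1 day.

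The cost is SAP wording and table-shell edits. No samples, visits or sample-size changes are needed.

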**Table 82:** **Abnormal Laboratory Results by Maximum Severity, Time Point, and Vaccination Group – AST\***

**Table 83:** **Abnormal Laboratory Results by Maximum Severity, Time Point, and Vaccination Group – ALT\***

**Table 84:** **Abnormal Laboratory Results by Maximum Severity, Time Point, and Vaccination Group - Total Bilirubin\***

**Table 85:** **Abnormal Laboratory Results by Maximum Severity, Time Point, and Vaccination Group - Blood Urea Nitrogen\***

**Table 86:** **Abnormal Laboratory Results by Maximum Severity, Time Point, and Vaccination Group – Creatinine\***

Abnormal Labs Related to Study Product:

**Table 87:** **Abnormal Laboratory Results Related to Study Product by Maximum Severity, Time Point, and Vaccination Group - Any Chemistry Parameter**

**Table 88:** **Abnormal Laboratory Results Related to Study Product by Maximum Severity, Time Point, and Vaccination Group - AST**

**Table 89:** **Abnormal Laboratory Results Related to Study Product by Maximum Severity, Time Point, and Vaccination Group - ALT**

**Table 90:** **Abnormal Laboratory Results Related to Study Product by Maximum Severity, Time Point, and Vaccination Group - Total Bilirubin**

**Table 91:** **Abnormal Laboratory Results Related to Study Product by Maximum Severity, Time Point, and Vaccination Group - Blood Urea Nitrogen**

**Table 92:** **Abnormal Laboratory Results Related to Study Product by Maximum Severity, Time Point, and Vaccination Group - Creatinine**

**Table 93: Laboratory Summary Statistics by Time Point and Vaccination Group - AST**

	Vaccination Group	N	Mean	Standard Deviation	Median	Min, Max
Baseline						
Results	Low Dose ChAd155-RG	x	xx.x	xx.x	xx.x	xx, xx
	High Dose ChAd155-RG (x1)					
	High Dose ChAd155-RG (x2)					
	Combined High Dose a ChAd155-RG					
	RABAVERT					
	Total					
Day 2 (1 Day Post Dose 1)						
Results	Low Dose ChAd155-RG					
	High Dose ChAd155-RG (x1)					
	High Dose ChAd155-RG (x2)					
	Combined High Dose a ChAd155-RG					
	RABAVERT					
	Total					
Change from baseline	Low Dose					
	High Dose ChAd155-RG (x1)					
	High Dose ChAd155-RG (x2)					
	Combined High Dose a ChAd155-RG					
	RABAVERT					
	Total					
Repeat for						
Day 8 (Pre-Dose 2)						
Day 16 (2 Days Post Dose 3)						
Day 22 (Pre-Dose 4)						
Max Severity Post Baseline						
Note: N = Number of subjects in the Safety Population with available results at specified time point.						
a Both high dose groups combined.						

Tables with similar format:

---

**Table 94:** **Laboratory Summary Statistics by Parameter, Time Point, and Vaccination Group - ALT**

**Table 95:** **Laboratory Summary Statistics by Parameter, Time Point, and Vaccination Group - Total Bilirubin**

**Table 96:** **Laboratory Summary Statistics by Parameter, Time Point, and Vaccination Group - Blood Urea Nitrogen**

**Table 97:** **Laboratory Summary Statistics by Parameter, Time Point, and Vaccination Group - Creatinine**

**14.3.5.2 Hematology Results****Table 98: Abnormal Laboratory Results by Maximum Severity, Time Point, and Vaccination Group - Any Hematology Parameter\***

Time Point	Vaccination Group	N	None		Mild/ Grade 1		Moderate/ Grade 2		Severe/ Grade 3		Any Severity	
			n (%)	95% CI	n (%)	95% CI	n (%)	95% CI	n (%)	95% CI	n (%)	95% CI
Baseline (Pre-Dose 1)	Low Dose ChAd155-RG	x	x (xx)	(xx, xx)	x (xx)	(xx, xx)	x (xx)	(xx, xx)	x (xx)	(xx, xx)	x (xx)	(xx, xx)
	High Dose ChAd155-RG (x1)											
	High Dose ChAd155-RG (x2)											
	Combined High Dose a ChAd155-RG											
	RABAVERT											
	Total											
Repeat for:												
Day 2 (1 Day Post Dose 1)												
Day 8 (Pre-Dose 2)												
Day 16 (2 Days Post Dose 3)												
Day 22 (Pre-Dose 4)												
Max Severity Post Baseline												

Note: The “Max Post Baseline” rows indicate the maximum severity of abnormal laboratory results experienced by each subject at any time point post baseline, including unscheduled assessments.

N = Number of subjects in the Safety Population; n = number of subjects with laboratory values in the respective category.

aBoth high dose groups combined.

